4.2.1.1.2 Maximum Intensity

Maximum overall intensity is derived from the daily intensities computed as described in Section 4.2.1.1.1 and is calculated as the maximum of the daily intensities over the period considered.

4.2.1.1.3 Presence

Presence is derived from the maximum overall intensity over the time period considered:

- None: No presence

- Grade 1, Grade 2, or Grade 3: Presence
- Missing or Unknown: Missing presence

Participants with at least one non-missing presence for a specific endpoint will be included in the analysis. Conversely, those without a non-missing presence will not be included in the analysis of the endpoint.

4.2.1.1.4 Time of Onset

Time of onset is derived from the daily intensities computed as described in Section 4.2.1.1.1. It corresponds to the first day with intensity of Grade 1, Grade 2, or Grade 3.

Note: If a reaction is not continuous (i.e., reaction occurs over two separate periods of time intervened by at least one daily intensity Missing or None) then the time of onset is the first day of the first occurrence.

Time of onset period is displayed as, D1-D4, D5-D8.

4.2.1.1.5 Number of Days of Occurrence During the Solicited Period

Number of days of occurrence over the period considered is derived from the daily intensities computed as described in Section 4.2.1.1.1. It corresponds to the number of days with daily intensities of Grade 1, Grade 2, or Grade 3. Number of days of presence on the solicited period with a specified intensity may also be derived.

4.2.1.1.6 Overall Number of Days of Occurrence

If a reaction is ongoing at the end of the solicited period, then the overall number of days of presence is derived from the daily intensities and the end date of the reaction after the end of the solicited period. The overall number of days of presence is:

- (End date - vaccination date) + (number of days of presence within the solicited period) - length of the solicited period + 1

If the end date is missing or incomplete (contains missing data), the overall number of days of presence will be considered as Missing.

4.2.1.1.7 Ongoing

Ongoing is derived from the last daily intensity of the solicited period computed as described in Section 4.2.1.1.1 and the maximum intensity on the ongoing period. The investigator's ongoing flag is not used because the measurement will determine the ongoing status of the reaction.

- Ongoing: if the last daily intensity of the solicited period is at least Grade 1 and the maximum intensity on the ongoing period is at least Grade 1
- Not ongoing: if the last daily intensity of the solicited period is None or the maximum intensity on the ongoing period is None.

- Missing: all other conditions (in this case, it is not included in the denominator of the ongoing analysis in the safety tables).

4.2.1.1.8 Vaccination

For participants having received 1 vaccine, solicited reactions will be assigned to the vaccine received. For participants having received the 2 concomitant administrations, solicited injection site reactions will be assigned to the vaccine injected on the same side as the solicited reaction, and solicited systemic reactions will be assigned to both vaccines.

4.2.1.2 Unsolicited AEs

4.2.1.2.1 Presence

An observation will be considered an event if it has at least a verbatim term and is not a Grade 0 intensity event.

Grade 0 events are not included in safety analysis but are included in separate listings.

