4.2.1.2.2 Intensity

Intensity will be derived according to the following classification: None, Grade 1, Grade 2, Grade 3, or Missing

If the unsolicited AE is measurable and its preferred term is part of the list of solicited reactions, then the measurement is derived based upon and following the same rule of the intensity scales defined in the protocol for that measurable injection site or systemic reaction. Note the intensity could be considered as “None” (not a reaction) in the analysis despite being considered a reaction by the investigator (e.g., swelling measurement >0 mm but < 25 mm in adults).

Intensity for the other unsolicited AEs will correspond to the value reported in the CRF.

The maximum intensity corresponds to the highest intensity for a unique term.

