4.2.1.2.6 Medically-Attended Adverse Event

An event will be considered as an MAAE if “Yes” is checked for “Is the event an MAAE?” in the CRF. MAAE will be analyzed within 21 days after vaccination, from D22 to 180 days after vaccination, and within 180 days after vaccination.

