4.2.1.2.7 Serious Adverse Events

An event will be considered as a serious event if “Yes” is checked for “Serious” in the CRF.

SAEs will be analyzed within 21 days after vaccination, from D22 to 180 days after vaccination, and within 180 days after vaccination.

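### A medically attended late local reaction under 25 mm drops out of the MAAE table, because the SAP's Grade 0 exclusion has no exemption for flagged events

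*SAP*

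**What the plan says.** Three parts of SAP section 4.2.1.2 (Unsolicited AEs) act in sequence.

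- **Intensity (4.2.1.2.2).** "Intensity will be derived according to the following classification: None, Grade 1, Grade 2, Grade 3, or Missing". The measurement is converted on the protocol scale under this condition: "If the unsolicited AE is measurable and its preferred term is part of the list of solicited reactions". The SAP accepts that this can overrule the site: "Note the intensity could be considered as “None” (not a reaction) in the analysis despite being considered a reaction by the investigator". Its example is a swelling above 0 but below 25 mm. All other unsolicited AEs keep the CRF grade.
- **Presence (4.2.1.2.1).** "An observation will be considered an event if it has at least a verbatim term and is not a Grade 0 intensity event". It adds: "Grade 0 events are not included in safety analysis but are included in separate listings".
- **Flagged events (4.2.1.2.6 to 4.2.1.2.8).** MAAEs, SAEs and AESIs are identified by a CRF tick-box. The SAE rule opens "An event will be considered as a serious event if", and the other two open in the same way. For timing, "MAAE will be analyzed within 21 days after vaccination", then from D22 to 180 days and over the full 180 days. None of the three mentions intensity or an exemption from the Presence rule.

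The endpoints in SAP Table 2.1 are the presence of SAEs, AESIs and MAAEs reported up to 6 months, with no intensity threshold. Protocol 10.2.1 counts SAEs among the unsolicited AEs and defines an MAAE by the participant seeking unplanned medical advice.

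**The concern.** The 25 mm and 38.0 °C floors belong to the grading of solicited reactions. Protocol 10.2.5.1.2 extends that scale to measurable unsolicited AEs, which is reasonable for grading. The SAP goes further and lets the scale decide whether an observation exists as an event at all. For an MAAE or SAE that is the wrong test: one is defined by seeking care, the other by outcome or medical importance, and neither depends on diameter.

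At stake is the tabulated count, and its confidence interval, for a stated safety endpoint. The exclusion can only lower that count. It also treats measurement oddly, because a swelling that was measured and found small is dropped while one that nobody measured is kept.

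**Working it through.** The plan gives no figure for this rule, so the check traces the text and then sizes one dropped event. The plan's only sample-size arithmetic reproduces: 100 × (1 − 0.05) = 95 evaluable per group (Protocol 9.2).

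**Inputs**

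| Input | Value | Source |
|---|---|---|
| Size floor, Grade 1 | 25 mm (erythema, swelling, induration, bruising) | Protocol Table 10.1 |
| Temperature floor, Grade 1 | 38.0 °C | Protocol Table 10.2 |
| CRF grades, other unsolicited AEs | Grades 1 to 3 only | Protocol 10.2.5.1.2 |
| Missing intensity | left missing | SAP 3.4.4.1.3 |
| Group size | about 100; 95 after drop-out | SAP 3.2; Protocol 9.2 |
| CI method | exact Clopper-Pearson, 95% | SAP 3.4.1 |

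**Step 1: does 'None' mean Grade 0?** The SAP never says so. The CRF scale has no grade below 1, so a derived 'None' is the only documented source of a Grade 0. SAP 4.2.2.6 filters unsolicited AEs leading to discontinuation to those of at least Grade 1 or missing, which excludes the same class. The inference is strong, but it remains an inference.

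**Step 2: apply the rule as written to example records.**

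| Unsolicited record | Derived intensity | Result |
|---|---|---|
| Swelling 20 mm, MAAE = Yes | None | listing only |
| Swelling 24 mm, Serious = Yes | None | listing only |
| Pyrexia, highest value 37.9 °C, MAAE = Yes | None | listing only |
| Swelling 25 mm | Grade 1 | counted |
| Pyrexia 38.0 °C | Grade 1 | counted |
| Swelling not measured, MAAE = Yes | Missing | counted |

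**Step 3: size of one dropped participant.** For x events in n participants, the lower limit is the 0.025 quantile of Beta(x, n − x + 1) and the upper limit is the 0.975 quantile of Beta(x + 1, n − x). The lower limit is 0 when x = 0.

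| x/n | Rate | 95% CI |
|---|---|---|
| 0/100 | 0.0% | 0 to 3.62% |
| 1/100 | 1.0% | 0.03 to 5.45% |
| 2/100 | 2.0% | 0.24 to 7.04% |
| 0/95 | 0.0% | 0 to 3.81% |
| 1/95 | 1.05% | 0.03 to 5.73% |

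Each participant whose only flagged event is derived as 'None' moves the group rate by 1/100 = 1.0 point, or 1/95 = 1.05 points.

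**Step 4: which flagged events can be reached?** Only the five measured terms, and an event with a solicited term is mainly unsolicited when it starts after D08.

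- *MAAE:* possible. The definition excludes solicited reactions, which leaves late, small local signs or sub-38.0 °C temperatures for which advice was sought.
- *SAE:* unlikely. Protocol 10.2.3 asks for the diagnosis rather than the sign where possible.
- *AESI:* close to empty. None of the five terms is on the list in Protocol 8.3.6.

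**The case against.** The case on the other side is substantial, and much of it stands.

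- **A reader might infer that the SAP contradicts itself.** It does not. The MAAE, SAE and AESI rules classify what already qualifies as an event under 4.2.1.2.1. That is a sequence, and 4.2.2.6 is consistent with it. The fault is that the sequence yields the wrong count for an endpoint without an intensity threshold.
- **A reader might infer that SAEs and AESIs are generally at risk.** Step 4 shows otherwise. In addition, Protocol 8.3.1 introduces the scale for non-serious unsolicited AEs, and an SAE without a grade or measurement would be Missing and kept. Protocol 10.2.5 does grade every AE, and SAP 4.2.1.2.2 is not limited to non-serious events, so the SAE route is narrow but open. A serious pyrexia with no value of 38.0 °C is a strained example, since the protocol asks for a temperature at any apparent fever and has the highest value recorded.
- **The events are not lost.** They go to separate listings, so they leave the table and its interval but stay in the report.
- **Using the scale is the protocol's choice.** This is true of grading. The protocol does not say that a reported MAAE below the scale stops being one.
- **One event falling to none is a chosen illustration.** MAAEs run for 6 months in adults aged 65 and older and include phone or e-mail contact, so they may not be rare. If 20/100 had one (an assumption), losing one gives 19/100, and the interval moves from 12.7 to 29.2% to 11.8 to 28.1%. No hypothesis is tested, so no decision rule changes.
- **Bias between arms.** Group 1 has two injection sites and the other groups have one, so exposure to the rule is unequal. The documents give nothing to quantify this, and it is not claimed as a measurable bias.

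**Conclusion.** The point holds in a narrow form. Followed as written, the SAP would drop a medically attended, sub-25 mm, late local reaction from the MAAE endpoint, and could in principle do the same to an SAE. The likely effect is a small number of MAAEs. The number is unknown because the documents give no rate. Each affected participant shifts a group rate by about 1 percentage point. The conclusion rests on reading a derived 'None' as Grade 0. If the sponsor meant something else, Grade 0 is undefined and still needs a definition. It is worth correcting because the error runs in one direction, affects a named safety endpoint and is cheap to remove. The documents do not support a claim that serious events will go unreported.

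**What to change.** 1. In SAP 4.2.1.2.1, define Grade 0 as a derived intensity of 'None'.
2. In the same section, add that events flagged Serious, AESI, MAAE or leading to study discontinuation are counted in their endpoint tables whatever the derived intensity. Show the intensity as 'None (below scale)' or Missing. Do not rely on a CRF grade: by the footnotes to Protocol Tables 10.1 and 10.2, sized reactions and fever are recorded as measurements and graded at analysis, so a CRF grade may not exist.
3. Align the filter for unsolicited AEs in SAP 4.2.2.6 (safety overview and SOC/PT tables), which now requires at least Grade 1 or missing.
4. Keep the Grade 0 exclusion for all other unsolicited AEs, and footnote any flagged event shown as below scale so that counts can be reconciled between tables.

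The cost is a few sentences in the SAP and one condition in the program. No new data are needed, because the events are already collected and destined for listings.

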4.2.1.2.2 Intensity

Intensity will be derived according to the following classification: None, Grade 1, Grade 2, Grade 3, or Missing

If the unsolicited AE is measurable and its preferred term is part of the list of solicited reactions, then the measurement is derived based upon and following the same rule of the intensity scales defined in the protocol for that measurable injection site or systemic reaction. Note the intensity could be considered as “None” (not a reaction) in the analysis despite being considered a reaction by the investigator (e.g., swelling measurement >0 mm but < 25 mm in adults).

Intensity for the other unsolicited AEs will correspond to the value reported in the CRF.

The maximum intensity corresponds to the highest intensity for a unique term.

4.2.1.2.3 Vaccination

For participants having received 1 vaccine, unsolicited AEs will be assigned to the vaccine received. For participants having received the 2 concomitant administrations, unsolicited injection site reactions will be assigned to the vaccine injected on the same side as the reaction, and other AEs will be assigned to both vaccines.

4.2.1.2.4 Time of Onset

Time of onset is derived from the start date of the unsolicited AE and the date of vaccination:

Time of Onset = start date of the unsolicited AE - date of vaccination + 1 (if D1 is the first vaccination day).

The time of onset is considered as missing only if one or both dates are missing or partially missing.

The unsolicited AEs will be analyzed “Within 21 days” after vaccination, which corresponds to AEs with a time of onset between D1 and D22 or missing. An AE with missing time of onset will be considered to have occurred just after the vaccination, so will be included in these tables.

Time of onset period is displayed as D1-D4, D5-D8, D9-D15, D16 or later, and Missing.

Note: Unsolicited AE that occurred before vaccination (negative time of onset) or with a time of onset higher than defined above will not be included in analysis but will be listed separately.

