3.4.4.1.4 Start Date and End Date

Missing or partially missing start dates or end dates for unsolicited AEs (including SAEs) will remain missing and not be imputed. If the start date is missing or partially missing, the time of onset will be considered missing. If either the start date or end date is missing or partially missing, the duration will be considered missing.

Missing or partially missing end dates for ongoing solicited AEs will remain missing and not be imputed.

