4.2.1.2.8 Adverse Events of Special Interest

An event will be considered as an AESI if “Yes” is checked for “Is the event an AESI?” in the CRF.

AESIs will be analyzed within 21 days after vaccination, from D22 to 180 days after vaccination, and within 180 days after vaccination.

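### Safety windows: an unsolicited event with a partial start date is counted within 21 days even when the recorded month rules that out, and an onset on D22 falls in both the early and the later window

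*SAP*

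**What the plan says.** On incomplete dates, SAP 3.4.4.1.4 states: "Missing or partially missing start dates or end dates for unsolicited AEs (including SAEs) will remain missing and not be imputed". It continues: "If the start date is missing or partially missing, the time of onset will be considered missing". SAP 4.2.1.2.4 repeats the rule ("The time of onset is considered as missing only if one or both dates are missing or partially missing") and defines the within-21-days analysis as one that "corresponds to AEs with a time of onset between D1 and D22 or missing". It then places the missing onsets: "An AE with missing time of onset will be considered to have occurred just after the vaccination, so will be included in these tables". The onset display has its own row for missing onset. A Note sends events before vaccination, or with an onset beyond the window, to a separate listing.

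On the 6-month classes, three sections set the same three windows:
- SAP 4.2.1.2.6: "MAAE will be analyzed within 21 days after vaccination, from D22 to 180 days after vaccination, and within 180 days after vaccination".
- SAP 4.2.1.2.7: "SAEs will be analyzed within 21 days after vaccination, from D22 to 180 days after vaccination, and within 180 days after vaccination".
- SAP 4.2.1.2.8: "AESIs will be analyzed within 21 days after vaccination, from D22 to 180 days after vaccination, and within 180 days after vaccination".

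None of these three sections mentions missing onset.

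Protocol 8.3.1 collects non-serious unsolicited AEs to D22, and SAEs, AESIs and MAAEs to D181. Protocol 10.2.1 counts SAEs among unsolicited AEs.

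**The concern.** There are two separate defects.

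(a) A start date with a known month and year but no day carries real information. The SAP discards it and files the event as if it began just after vaccination. Early assignment is a sensible conservative convention when the known parts allow an early onset. When they exclude one, it is misclassification. The Note in 4.2.1.2.4 does not catch such an event, because it acts on a computed onset and a partial date has none. The SAP also does not say whether the event would enter the later window as well.

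(b) D22 is the last day of the early window and the first day of the later one, so an event starting that day is tabulated in both.

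At stake is the accuracy of the 21-day tables in the final analysis. Twenty-one days is the period named in the safety objective. Under (b), event counts in the early and later windows would sum to more than the 180-day count.

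**Working it through.** **Inputs.** Onset = start date − vaccination date + 1 (SAP 4.2.1.2.4). Collection of SAEs, AESIs and MAAEs runs to D181 (Protocol 8.3.1). The final telephone contact is at D181 with a window of +14 days (Protocol 1.3). Each arm has about 100 participants (SAP 3.2).

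**Reproducing the SAP's window.** An event 21 days after vaccination has onset 21 + 1 = D22, which agrees with the SAP's D1-D22. An event 180 days after has onset 180 + 1 = D181, which agrees with the end of collection.

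**Overlap (b).** As written, D1-D22 has 22 days and D22-D181 has 160. The sum is 182, against 181 days in D1-D181; the surplus day is D22. With the later window starting at D23, 22 + 159 = 181, with no gap and no overlap.

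**Partial date (a), worked example.** Assume vaccination on 4 August 2021. Then D22 = 25 August 2021, D181 = 31 January 2022 and D195 = 14 February 2022.

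| Recorded start | Possible onset | Current SAP rule | Known-parts rule |
|---|---|---|---|
| August 2021 | D1-D28 | within 21 days | within 21 days (compatible) |
| October 2021 | D59-D89 | within 21 days | D23-D181 |
| February 2022 | D182-D195 | within 21 days | listed separately |

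The last column is the rule proposed under the fix. The February range stops at D195, the last day on which the call may be made.

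**How often the month alone settles it.** Assume that a partial date has a known month and that each onset day from D23 to D181 (159 days) is equally likely. The month excludes D1-D22 whenever it is later than the month containing D22.
- Worst case: D22 is the first of a 31-day month, so 30 later days share its month. 159 − 30 = 129, and 129/159 = 81%.
- Best case: D22 is the last day of a month, giving 159/159 = 100%.
- Averaged over 365 vaccination dates: 90.7%.

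This is conditional on a late event having such a date. It says nothing about how often that happens.

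**Upper bound.** The call can be made as late as 181 + 14 = D195. The days D182-D195 reach a new calendar month when D181 falls in the last 14 days of a month: 12 × 14 = 168 of 365 vaccination dates (46%).

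**Effect of one misfiled event in an arm of 100** (Clopper-Pearson 95% CI; the 10/100 base is an assumption):

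| Count | Estimate | 95% CI |
|---|---|---|
| 0/100 | 0% | 0 to 3.62% |
| 1/100 | 1% | 0.03 to 5.45% |
| 10/100 | 10% | 4.90 to 17.62% |
| 11/100 | 11% | 5.62 to 18.83% |

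**The case against.** The strongest reply concerns scope. The missing-onset sentence sits in the definition of the 21-day unsolicited-AE table, and 4.2.1.2.6 to 4.2.1.2.8 set their own windows without it. The Note in 4.2.1.2.4 drops onsets after D22, which cannot apply to classes analysed to 180 days, so that section was evidently not written as the full rule for 6-month events. This stands as far as it goes: for the dedicated tables the SAP is not explicit. But 3.4.4.1.4 names SAEs and the protocol counts SAEs as unsolicited AEs, so a late SAE with a partial date can enter the general 21-day table in any case. The three window sections fall under the same parent section and reuse the same term. If the rule does not reach them, the SAP has no placement rule there at all. Either reading needs a sentence.

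The second reply is that the rule is conservative, visible in the missing-onset row, and seldom triggered. SAEs are reported within 24 hours, AESIs are captured as SAEs, and a Memory Aid supports recall of MAAEs. This stands on frequency, which cannot be shown and may be zero. The missing-onset row reveals an incomplete date but does not correct the window.

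The third reply is that participant counts would not add up across windows even with a D23 start, since one person can have events in both. That is correct, so the additivity point applies to event counts. A D22 event is still tabulated twice.

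It can also be said that one sentence barring such events from the 21-day tables would be enough. It would remove the misfiling, but would leave open where the event goes instead.

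**Conclusion.** The concern holds and is minor. The D22 overlap is certain on the text. The partial-date misfiling follows from the stated rules for SAEs in the general 21-day table; for the dedicated SAE, AESI and MAAE tables it rests on the likelier of two readings. It is most plausible for MAAEs, because after V02 the only scheduled contact is the D181 call.

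One misfiled event shifts a 21-day figure by about one percentage point in an arm of 100. The first-step D22 analysis and the 180-day totals for events that began by D181 are largely unaffected by (a). The overlap in (b) inflates neither the 21-day rate nor the 180-day total. No hypothesis is tested, so this is a matter of tabulation accuracy and does not threaten a conclusion. The documents give no count of partial dates or D22 onsets, so the realised effect cannot be computed.

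**What to change.** 1. In SAP 4.2.1.2.6, 4.2.1.2.7 and 4.2.1.2.8, set the windows to D1-D22, D23-D181 and D1-D181.
2. In SAP 3.4.4.1.4 and 4.2.1.2.4, add a rule for SAEs, AESIs and MAAEs with an incomplete start date:
   - keep early assignment when the known parts are compatible with D1-D22, or when the date is wholly unknown;
   - assign to D23-D181 when the known parts exclude onset by D22 but are compatible with onset by D181;
   - list separately when the known parts show onset before vaccination or after D181.

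   The D1-D181 table holds the events of both windows. Footnote the number of incomplete dates in each window.
3. Optionally, cross-refer the Note in 4.2.1.2.4 to 4.2.1.2.6-4.2.1.2.8, so that it is not read as removing late SAEs, AESIs and MAAEs from analysis.

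The cost is short wording edits in five SAP sections and minor programming. No new data are needed.
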